7.2.1 Screening

After written consent has been obtained, subjects will be screened in order to assess eligibility for study participation. All screening procedures must be performed within 28 days prior to start of investigational product administration, unless otherwise noted.

Subjects who meet the inclusion and exclusion criteria will be eligible to be enrolled in the study. If a subject has not met all eligibility criteria at the end of the 28-day window, the subject will be registered as a screen failure. Subjects who screen fail may be eligible for re-screening at the investigator's discretion after consultation with Amgen (see also below for details on re-screening).

Laboratory assessments used to determine subject eligibility may be repeated once for confirmation during the 28-day screening period before the subject is considered a screen failure. If laboratory assessments are repeated during the screening period, the result of the last sample taken prior to start of treatment with AMG 510 will be taken into account for determination of subject eligibility.

The following procedures are to be completed during the screening period at the time points designated in the Schedules of Assessments (Table 2, Table 5, and Table 6).

Assessments that were performed as standard of care prior to signature of informed consent, but within 21 days prior to start of treatment with AMG 510 can be used as screening assessments and do not need to be repeated to confirm subject eligibility.

Rescreening:

Subjects may be rescreened up to 2 times at the discretion of the investigator, after consultation with Amgen. The subject must be re-consented if a rescreening attempt occurs more than 30 days after the original signing of the ICF.

Rescreened subjects must be documented as screen failed in the subject's medical record and subsequently documented as rescreened. Subjects will retain the same subject identification number assigned at the time of initial screening. Once the subject is recorded as rescreened, a new 28-day screening window will begin. The following

assessments do not have to be repeated during rescreening, if they were performed as standard of care or during the initial screening attempt within the time frames specified below:

- Hepatitis serology does not need to be repeated if it was performed within 6 weeks prior to start of treatment with AMG 510.
- Imaging assessments do not need to be repeated if they were performed within 4 weeks prior to start of treatment with AMG 510.
- **Central confirmation of KRAS G12C status (if applicable)**

Any other assessments do not need to be repeated if they were performed within 21 days prior to start of treatment with AMG 510.

7.2.2 Treatment

Treatment begins on Day 1 **of cycle 1** when the first **dose of** investigational product is administered to a subject.

During clinic visit days all protocol-required predose assessments have to be performed prior to administration of AMG 510.

Results of any predose laboratory tests will not have to be available before the administration of AMG 510. Laboratory assessments that were done within 24 hours prior to AMG 510 administration do not need to be repeated.

AMG 510 will be dispensed to subjects at the beginning of each cycle and the subjects are required to bring the bottle of AMG 510 to clinic during clinic visit days. AMG 510 administration should be done in the clinic after all pre-dose assessments have been performed during clinic visit days.

[REDACTED]

For phase 1, a **paper** diary will be provided to subjects at the beginning of each cycle and the study staff will provide guidance to the subjects on how to complete the diary.

For phase 2, once a subject is confirmed as eligible and becomes enrolled, site study staff will assign and provide an eDiary (to capture compliance with AMG 510 administration). The site study staff will train the subject on how to use the eDiary (eg, turning on/off, charging, navigating screens, transmitting data, contacting the help desk for technical assistance) and complete the questions. The subject will be instructed to interact with the eDiary every day and to bring the eDiary to every study visit.

Please refer to the eDiary manual for additional details.

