209. Anti-tumor therapy (chemotherapy, antibody therapy, molecular targeted therapy, retinoid therapy, hormonal therapy [except for subjects with breast cancer], or investigational agent) within 28 days of study day 1; concurrent use of hormone deprivation therapy for hormone-refractory prostate cancer or breast cancer is permitted
210. Therapeutic or palliative radiation therapy within 2 weeks of study day 1. Subjects must have recovered from all radiotherapy related toxicity.
211. Currently enrolled in another investigational device or drug study, or less than 28 days since ending another investigational device or drug study(s), or receiving other investigational agent(s)
212. Other investigational procedures are excluded
214. Major surgery within 28 days of study day 1
215. **Monotherapy with AMG 510: Men and women of childbearing potential (WOCBP) who are unwilling to practice acceptable methods of birth control during treatment and for at least 37 days (women) or 97 days (men) after receiving the last dose of AMG 510. Acceptable methods of highly effective birth control for women include sexual abstinence (refraining from heterosexual intercourse); vasectomy (women with a single male sexual partner) with testing showing there is no sperm in the semen; bilateral tubal ligation or occlusion; or intrauterine device. Acceptable methods of birth control for men include sexual abstinence (refraining from heterosexual intercourse); vasectomy with testing showing there is no sperm in the semen; bilateral tubal ligation or occlusion in the partner; or a condom (the female partner should also consider a form of birth control).**
- 

Approved

[REDACTED]

Note: A woman is considered of childbearing potential (WOCBP), ie, fertile, following menarche and until becoming postmenopausal unless permanently sterile. Permanent sterilization methods include hysterectomy, bilateral salpingectomy, and bilateral oophorectomy. A postmenopausal state is defined as no menses for 12 months without an alternative medical cause. A high follicle stimulating hormone level in the postmenopausal range may be used to confirm a postmenopausal state in women not using hormonal contraception or hormonal replacement therapy. However, in the absence of 12 months of amenorrhea, a single follicle stimulating hormone measurement is insufficient.

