216. Women who are lactating/breast feeding or who plan to breastfeed while on study through 37 days [REDACTED] after receiving the last dose of study drug.
217. Women with a positive pregnancy test.
218. Women planning to become pregnant while on study through 37 days [REDACTED] after receiving the last dose of study drug
219. Subject has known sensitivity to any of the products to be administered during dosing
220. Subject will not be available for protocol-required study visits or procedures, to the best of the subject and investigator's knowledge
221. Subject has any kind of disorder that, in the opinion of the investigator, may compromise the ability of the subject to give written informed consent and/or to comply with all required study procedures
222. History or evidence of any other clinically significant disorder, condition or disease (with the exception of those outlined above) that, in the opinion of the investigator or Amgen physician would pose a risk to subject safety or interfere with the study evaluation, procedures or completion
223. Use of known cytochrome P450 (CYP) 3A4 and MATE1 sensitive substrates (with a narrow therapeutic window), within 14 days or 5 half-lives of the drug or its major active metabolite, whichever is longer, prior to study day 1 that was not reviewed and approved by the principal investigator and the Amgen medical monitor
224. Use of strong inhibitors of CYP3A4 or P-gp (including herbal supplements such as Goldenseal) within 14 days or 5 half-lives (whichever is longer) or grapefruit juice or grapefruit containing products within 7 days prior to study day 1 that was not reviewed and approved by the principal investigator and the Amgen medical monitor.
225. Use of strong inducers of CYP3A4 (including herbal supplements such as St. John's wort) within 14 days or 5 half-lives (whichever is longer) prior to study day 1 that was not reviewed and approved by the principal investigator and the Amgen medical monitor.

Approved

227. History of other malignancy within the past 2 years, with the following exceptions:
- Malignancy treated with curative intent and with no known active disease present for ≥ 2 years before enrollment and felt to be at low risk for recurrence by the treating physician.
 - Adequately treated non-melanoma skin cancer or lentigo maligna without evidence of disease.
 - Adequately treated cervical carcinoma in situ without evidence of disease.

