Footnotes defined on last page of [Table 6](#).

Table 5. Schedule of Assessment: Phase 2 Study Visits Through Cycle 1 Treatment

	Screening	Treatment																					
Cycle		1																					
Day	-28 to 1	1								2		8						9		15			
Hours (relative to dosing)		pre	0	0.25	0.5	1	2	4	6	pre	0	pre	0	0.25	0.5	1	2	4	6	pre	0	pre	0
Patient-reported Outcomes																							
EORTC QLQ C30		X																					
QLQ LC13		X																					
NSCLC SAQ		X																					
QLQ PAN26		X																					
PRO-CTCAE		X																					
EQ-5D-5L		X																					
GP5 FACT-G		X																					
Laboratory^d																							
Chemistry	X	X										X											X
HbA1c	X																						
Hematology	X	X										X											X
Coagulation	X	X										X											X
Urinalysis ^e	X	X										X											X
Serum pregnancy test ^f	X																						
Urine pregnancy test^f		X																					
HIV	X																						
Hepatitis serology	X																						

Approved

Footnotes defined on last page of [Table 6](#).

Table 5. Schedule of Assessment: Phase 2 Study Visits Through Cycle 1 Treatment

	Screening	Treatment																					
Cycle		1																					
Day	-28 to 1	1								2		8								9		15	
Hours (relative to dosing)		pre	0	0.25	0.5	1	2	4	6	pre	0	pre	0	0.25	0.5	1	2	4	6	pre	0	pre	0
DOSING																							
AMG 510 ⁹		←----->																					
IMAGING ASSESSMENTS																							
Radiological imaging, (CT/MRI) and tumor assessment ^h	X																						
MRI brain ⁱ	X																						
PK ASSESSMENTS																							
AMG 510 PK (Group A) ^j		X	X	X	X	X	X	X	X	X		X		X	X	X	X	X	X	X			
AMG 510 PK (Group B) ^j		X				X		X															
BIOMARKER SAMPLES																							
Tumor markers at site ^k		(X)																					
Plasma ctDNA ^l		X										X											
Cell pellet from plasma ^m		X																					

Approved

Footnotes defined on last page of [Table 6](#).

Table 5. Schedule of Assessment: Phase 2 Study Visits Through Cycle 1 Treatment

	Screening	Treatment																					
Cycle		1																					
Day	-28 to 1	1							2		8						9		15				
Hours (relative to dosing)		pre	0	0.25	0.5	1	2	4	6	pre	0	pre	0	0.25	0.5	1	2	4	6	pre	0	pre	0
BIOMARKER SAMPLES Cont.																							
Serum		X										X											
PB Paxgene RNA		X										X											
Stool sample ⁿ		X																					
BIOMARKER DEVELOPMENT																							

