Additional procedures deemed necessary as part of standard of care or as required by local laws and regulations may be performed at the Investigator's discretion.

Table 7. List of Analytes

Local Laboratory			Central Laboratory
Chemistry	Hematology	Coagulation	PK and Biomarker
Sodium	Hemoglobin	PT or INR	PK sampling
Potassium	Hematocrit	aPTT Fibrinogen	Plasma ctDNA
Chloride	Mean corpuscular volume	D-Dimer	Plasma cell pellet
Bicarbonate Total protein	Platelets		Serum
Albumin	RBC		PB Paxgene RNA
Calcium	White blood cell Differential		Antibody
Magnesium	• Total neutrophils		Tumor biopsy ^c
Phosphorous	• Eosinophils		
Glucose	• Basophils		
Blood urea nitrogen	• Lymphocytes		
Urea ^a	Monocytes		
Creatinine			
Total creatine kinase	Serology ^b	Urinalysis	
Total bilirubin	HepBsAg	Specific gravity, pH,	
Direct bilirubin	HepCAb	Blood protein,	
Serum or Urine	HIV	glucose, bilirubin,	
Pregnancy		WBC, ketones,	
Alkaline phosphatase	Tumor markers	sodium, potassium	
Alanine aminotransferase	-Carcinoembryonic embryonic antigen (CEA)	RBC, epithelial cells, bacteria	
Aspartate aminotransferase	-Carbohydrate antigen (CA 19-9)	Microscopic exam:	
HbA1c	-Cancer antigen (CA 125)	• Cellular casts	
		• Granular casts	
		• Hemoglobin casts	
		• Hyaline casts	
		• Mixed casts	

Footnotes defined on next page of this table

Approved

HbA1c = hemoglobin A1c; HepBsAg = hepatitis B surface antigen; HepCAb = hepatitis C antibody; INR = international normalized ratio; LDH = lactate dehydrogenase; PB = peripheral blood; PK = pharmacokinetics; PT = prothrombin time; PTT = partial thromboplastin time; RBC = red blood cell count; WBC = white blood cell count.

^a Urea collection is acceptable in absence of BUN.

^b Hepatitis B surface antigen, hepatitis C antibody, PCR for Hepatitis C RNA (if Hepatitis C antibody is positive), and HIV assessments.

^c Archived tumor tissue is acceptable. If archived tumor tissues is not available, a tumor biopsy should be performed prior to treatment.

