- Futility/efficacy thresholds are added to monitor antitumor activities in phase 1 expansion to provide guidance to DLRM for determining RP2D and continuing to phase 2.
- Revision to use standard RECIST 1.1 for analysis of tumor response.

Updates to Phase 2:

- Revised patient population for NSCLC and CRC as defined by the eligibility criteria in terms of the extent of prior therapies.
- Clarified that twice-daily dosing cohort (phase 1 part 1b) will only be initiated after completion of preliminary food effect evaluation.
- Sample sizes for NSCLC, CRC are adjusted based on new benchmark rates
 - For NSCLC, revised the benchmark rate to 23% to exclude from the lower limit of the 95% confidence interval for observed ORR.
 - For CRC, revised the benchmark rate to 10% to exclude from the lower limit of the 95% confidence interval for observed ORR.

- Clarified that efficacy analysis will be performed using only “Phase 2” portion. Language pertaining to pooling subjects at RP2D from phase 1 and phase 2 for efficacy analysis is removed.
- Removed interim analysis for efficacy.
- Futility interim analysis in phase 2 portion is updated to allow continuous monitoring using Bayesian predictive probability method.
- Revision to use standard RECIST 1.1 for analysis of tumor response.
- Additional changes were made to the protocol with the following rationales.
- Time to response was added as an secondary endpoint in all phases to describe timing aspect of AMG 510 response profile.
- Removed the inclusion criteria requirement for alkaline phosphatase . Alkaline phosphatase (ALP) is often elevated in advance solid tumor with bone or liver metastasis and may not reflect liver function required to participate in the clinical trial when other liver function parameter criteria (AST, ALT, INR, Bilirubin) are met.
- Clarification of the inclusion criteria 215 pertaining birth control methods in accordance to Clinical Trial Facilitation and Coordination Gropu (CTFG) guidance.
- [REDACTED]
- [REDACTED]
- [REDACTED]
- [REDACTED]
- [REDACTED]
- [REDACTED]
- [REDACTED]
- [REDACTED]
- Additional patient-reported outcomes (NSCLC SAQ and GP5 FACT-G) were added to fully understand the impact of treatment on patients from their perspective.
- Addition of urine pregnancy test on day 1 of every cycle in female subjects with child bearing potential to meet CTFG guidance related to pregnancy testing in clinical trials.

Statistical Analysis Plan

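### In phase 2, section 7.2.2 lets the first dose be given before the cycle 1 day 1 pregnancy test result is known, so it can rest on a screening test up to 28 days old

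*Supplement*

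**What the plan says.** Protocol Amendment 3, section 7.2.2, requires the predose assessments of a clinic day to be carried out before AMG 510 is given. It then separates performing a test from knowing its result: "Results of any predose laboratory tests will not have to be available before the administration of AMG 510". No exception appears in the visible text.

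For phase 2, Table 5 (section 7.1) has a row "Urine pregnancy test" in its laboratory block, marked predose on cycle 1 day 1, for women of childbearing potential only. The serum test in the same table is marked at screening. Table 7 (section 7.2) lists pregnancy testing, "Serum or Urine", among the local laboratory analytes. The Summary of Changes gives the purpose of the urine test: "Addition of urine pregnancy test on day 1 of every cycle in female subjects with child bearing potential to meet CTFG guidance".

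On timing, section 7.2.1 says "All screening procedures must be performed within 28 days prior to start of investigational product administration", unless otherwise noted. Standard-of-care assessments made before consent but "within 21 days prior to start of treatment with AMG 510 can be used as screening assessments". Exclusion 217 in section 4.2 reads "Women with a positive pregnancy test" and names neither the type of test nor a time point.

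**The concern.** The cycle 1 day 1 test is the last check before a possible fetal exposure. If the first tablet may be taken before anyone has read the result, the test can stop later doses but may fail to prevent the first one.

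The protocol itself treats pregnancy as serious. It is an exclusion (217), a reason for removal from treatment (8.3.1) and a bar to further doses (9.3). Section 2.3.3 reports exploratory genetic toxicology in which AMG 510 was negative in the Ames assay but positive for clastogenicity in vitro. That is limited evidence, but enough to make a read result worth having. Stopping later doses cannot undo an exposure that has already happened.

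**Working it through.** No sample size, power or error rate is involved. The check is a reading of the text plus one interval.

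**Step 1: does the waiver reach this test?** The sentence in 7.2.2 covers every predose laboratory test. Table 5 puts the urine pregnancy test in the laboratory block, in the predose column of cycle 1 day 1. Table 7 classes pregnancy testing as a local laboratory analyte. On both counts it is a predose laboratory test, so the waiver applies.

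**Step 2: does any other visible text require the result before the first dose?**

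| Provision | What it does | Why it does not close the gap |
|---|---|---|
| 7.2.2, predose assessments | Requires the test to be done | Does not require it to be read |
| Exclusion 217 | Excludes a woman who tests positive | Works on day 1 only if the result has been seen |
| Section 5 | Enrollment follows the investigator's eligibility decision | That decision can rest on the screening serum test |
| 7.2.1, repeated laboratory tests | The last pre-treatment sample counts for eligibility | Covers repeats during screening; does not name the day 1 urine test or require its result |
| Footnote d of Tables 5 and 6 | Allows testing within 24 hours before day 1 | Governs when the sample is taken |
| Exclusion 215 | Requires willingness to use contraception during treatment and for 37 days after | States no duty for the screening interval |
| Exclusion 218 | Excludes women planning pregnancy on study | Does not cover an unplanned conception |
| Section 9.3 | Stops later doses once pregnancy is known | Cannot act on the first dose |

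None of these requires the result.

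**Step 3: how old can the last known result be at first dose?**

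- Screening serum test: up to 28 days (7.2.1; Table 5 screening column, day -28 to 1).
- Standard-of-care test from before consent: up to 21 days (7.2.1).
- With a required day 1 result and the 24-hour allowance: about 1 day.

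The differences are 28 - 1 = 27 days and 21 - 1 = 20 days. Section 7.2 allows treatment start to slip by up to 7 days with sponsor approval, but does not say that this extends the 28-day limit, so it is not added.

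**Step 4: how many women?** The documents do not give the number of women of childbearing potential. Section 2.6.2.1 gives a mean age of 53 years for the women among the first 22 phase 1 subjects, which suggests few.

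**The case against.** The strongest reply is that a site would not read 7.2.2 this way. Exclusion 217 has no time limit, the Table 5 screening column runs up to day 1, and for repeated screening tests the last sample before treatment decides eligibility. A site could reasonably treat the day 1 pregnancy test as an eligibility result and the 7.2.2 sentence as relief for routine safety laboratory tests. A urine test done locally may also be read at once. On this view the defect is a tension between an eligibility rule and a convenience sentence.

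Much of that is fair as a description of likely practice. It does not supply the missing rule: none of these provisions overrides the waiver, which is stated without limit.

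Three other points against the concern stand:

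- The 27-day difference is the age of a result, not a risk. Harm needs a conception that the screening test missed, a urine test that would be positive on day 1, and a dose given before it is read. The documents give none of these probabilities and no reading time.
- Unseen text could contain an exception: one block of 7.2.2 is redacted, and section 7.4 sends laboratory assessments to a manual that is not shown.
- The history does not show an oversight. Amendment 1 already listed pregnancy tests among the treatment-period laboratory assessments beside the same waiver.

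**Conclusion.** The point holds for phase 2, on the visible text. Followed as written, section 7.2.2 lets a woman of childbearing potential take her first dose with her most recent known pregnancy result up to 28 days old, or up to 21 days if a pre-consent standard-of-care test was used. The 28 days is an outer limit, not a typical value. The event is expected to be rare, few women are likely to be affected, and neither the endpoints nor the analysis is touched. The clarification is worth making because a stated rule can defeat a safety check and the remedy is very cheap.

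A reader might infer more than this. The documents do not support any of the following:

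- **That sites are told to dose without the result, or would do so.** The text permits it and does not direct it.
- **That the same gap is shown in phase 1.** Section 7.2.2 governs both phases, but the laboratory rows of Table 2 in Amendment 3 are not in the available text, so a phase 1 test on cycle 1 day 1 cannot be confirmed.
- **That a known number of doses is at stake in later cycles.** That depends on how soon a result is read, which is nowhere stated.

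Confidence is medium, because of the redacted block and the unseen manual.

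**What to change.** Add one sentence to section 7.2.2 and leave the waiver unchanged for all other predose laboratory tests:

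*Exception (phase 2, and phase 1 where a cycle 1 day 1 pregnancy test is scheduled): for women of childbearing potential, a negative result of the cycle 1 day 1 pregnancy test, which may be done within 24 hours before dosing, must be known before the first dose of AMG 510.*

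This adds no test and no visit. The cost is an occasional short wait on day 1, which local testing and the 24-hour allowance can largely avoid. Waiting loses no scheduled dose, because treatment begins only when the first dose is given. The wording is confined to the first dose: on later cycles a wait could cost a dose under the 6-hour skip rule in section 6.1.1.1.
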